Group 1+2+3 were randomized 1:1:1. As a cross-over designed study, PD patients could swap groups once a therapy- tranche has successfully been completed (i.e. BL, intensive therapy, 4 weeks Follow-up, 6 months Follow-up assessments), see Figure 1.

Group 4 were healthy elderly, who did not receive any therapy and participated once.

- Group 1: rhythmic Speech language Therapy (rSLT)
- Group 2: rhythmic Balance-Mobility Training (rBMT)
- Group 3: 'Waiting List', PD patients receiving no therapy
- Group 4: Healthy Controls (HC)

[figure not shown]

Figure 1. Study Design

7. Testing

Testing took place at baseline (BL), at 4 weeks (T1, directly after the end of intensive treatment) and at 6 months (T2 Follow-up).

a. Medical Examination (only at Baseline)

- i. Medical Examination regarding PD-dementia
- ii. Drug/Alcohol Abuse
- iii. Weight, Height, BMI
- iv. Medications
- v. UPDRS – Unified Parkinson's Disease Rating Scale-I (1/1)
- vi. Modified Neurologic Examination according to Hoehn & Yahr
- vii. Falls Efficiency Scale-1 (FES-1)

i. Speech-Language Tests with simultaneous PRAAT Recording (BL, T1, T2)

- i. Reading 'the northwind and the sun'
- ii. Aachner Aphasia Test (AAT): Spontaneous speech
- iii. AAT: Repeating
- iv. AAT: Naming

- v. Regensburgerwortflüssigkeitstest (RWT) complete
- vi. Comprehension of language-specific cues (Gardenpath Experiment)

b. Motor Tests

- One-leg and Tandem standing test (timed via chronometric stop watch in seconds)
- Parkinson Orientated Mobility Assessment (POMA)
- Walking 6 Meters (timed and counting steps)

c. Near-Infrared Spectroscopy (NIRS) (only at BL)

d. Neuropsychological tests/ psychiatric questionnaires (BL, T1 and T2)

Neuropsychological Tests:

- i. MOCA – Montreal Cognitive Assessment
- ii. Clock Test
- iii. CERAD – Boston Naming Test
- iv. CERAD – Word Retrieval (Animals)
- v. BVL – Basel Verbal Learning Test
- vi. BVL – Basel Verbal Learning Test
- vii. ROCF - Rey-Osterrieth Complex Figure
- viii. BVL - Basel Verbal Learning Test
- ix. BVL - Basel Verbal Learning Test - Recognition
- x. Word retrieval (S-Words)
- xi. TMT - Trail Making Test A
- xii. Trail Making Test B
- xiii. Stroop Test
- xiv. WMS-R - Verbal Digit Span
- xv. WMS-R - Corsi Blocks
- xvi. Mosaik-Test
- xvii. BVMT-R – Brief Visuospatial Memory Test-Revised
- xviii. TAP – Alertness
- xix. TAP - Divided Attention
- xx. Delayed Recall BVMT-R
- xxi. Recognition BVMT-R
- xxii. Tulia

Psychiatric Self-Rating Questionnaires:

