- ii. BDI – Beck's Depression Inventory (1/2)
- iii. BAI – Beck Angst (Fear) Inventar
- iv. MSS – Manie-Selbstbeurteilungsskala (Mania) (1/2)
- v. OCIR – Obsessive-Compulsive Inventory-Revised
- vi. BIS-11 – Barrat-Impulsiveness-Scale (1/2)
- vii. PDQ-39 – Parkinson Quality of Life Questionnaire
- viii. NEO-FFi-30 Items

- ix. AES-S – Apathy Evaluation Scale
- x. PFS-16 – Parkinson-Fatigueskala
- xi. Lebensqualitätsfragebogen (SeiQoI-DW)
- xii. IQ-Code – Questionnaire of cognitive abilities in elderly

8. Interventions

No drugs involved. While speech-language therapy is an established intervention programme in clinical and therapeutic practices, the rhythmic balance-mobility-training (rBMT) has been developed specifically to prevent mobility and balance issues in PD patients and has been evaluated scientifically (see *Parkinson Schweiz* <http://www.redance.ch/page/wirkung/sturzpraevention.html>).

Note that whether or not DBS is performed on a patient is dependent on multiple criteria and can only be decided by the medical team consisting of neurologists, neurosurgeon and neuropsychologists/ psychiatrists. Whether or not DBS is performed on a patient is not part of the study, as it is a normal medical procedure to cure dyskinesia and other motor symptoms arising in Parkinson's disease.

rSLT	
Contents	
 I. 3x 45 Minute sessions per week II. Empathic relationship between patient-therapist III. Specific exercises for the perception and improvement of respiration, phonation, articulation and body posture IV. Rhythmic Exercises according to 'Accent Method' by Sven Smith (1935, 1976)

rBMT	
Contents	
 • 3 x 45 minute sessions per week. • per session: at least 10 songs had to be danced, each with a length ranging from 1:47 - 3:25 Minutes per song. • 1st Week: Level 1. • 2nd Week: Level 1+2. • 3rd Week: Level 2. • 4th Week: Level 2+3.

7. Statistical Analysis

To calculate group differences (i.e. rSLT, rBMT, NT, HC) several univariate ANOVA with post-hoc Bonferroni corrections were performed.

Relationships between speech and gait variables were computed with Spearman's correlations (significance level $p < .05$). The level of statistical significance was set at $p < .05$.

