Changes in performance were analyzed with the reliable change score (RC). According to Jacobson and Truax (1991) scores are compared on a participant-individual level (e.g. BL with 4 weeks FU, and BL with 6 months FU). Positive scores indicate an improvement in performance, and negative scores indicate a worsening of performance. The RC shows whether a difference in performance is statistically significant on the basis of the reliability of the measurement. Thus, the reliable change score is equivalent to computing a z-score based on standard deviation units.

Further group comparisons are based on the RC scores. All statistical analyses were conducted with SPSS and R. All results are presented with effect sizes.

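### Arms are compared on reliable change scores without baseline adjustment, which costs precision, and the plan misdescribes the scale of that score

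*Combined protocol and SAP*

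**What the plan says.** Section 7, Statistical Analysis, names one method for group differences: "several univariate ANOVA with post-hoc Bonferroni corrections were performed". No baseline covariate appears there or elsewhere.

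Change is handled by the RC score at the level of the individual: "scores are compared on a participant-individual level (e.g. BL with 4 weeks FU, and BL with 6 months FU"). Its basis is given as "The RC shows whether a difference in performance is statistically significant on the basis of the reliability of the measurement", followed by the conclusion "Thus, the reliable change score is equivalent to computing a z-score based on standard deviation units". Then: "Further group comparisons are based on the RC scores".

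No RC formula, reliability coefficient, source of the SD, cut-off or allowance for practice is stated.

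On design, section 6 (Randomization) allocates three Parkinson's arms 1:1:1, one of them untreated: "Group 3: 'Waiting List', PD patients receiving no therapy". The healthy controls took part once, so they have no change score. Section 7 (Testing) sets three occasions: baseline, 4 weeks and 6 months.

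**The concern.** Three things need separating.

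- **Arm comparison.** An RC score is a change score divided by a constant. If one constant is used per test, ANOVA on RC is the same test as ANOVA on raw change. The baseline value then enters with a fixed coefficient of 1 instead of the coefficient the data support. In arms of about 23 patients, precision is lost, and any chance baseline difference carries into the result through regression to the mean.
- **Description of the score.** RC divides change by the standard error of the difference, which depends on reliability. An SD-unit z-score divides by the SD. The plan calls them equivalent, so a reader cannot tell what a given RC value means.
- **Individual calls.** The same tests are repeated within 4 weeks and again at 6 months. A gain from familiarity counts towards reliable improvement unless it is removed.

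At stake are the power of the therapy contrasts and the meaning of any reported proportion of improved patients.

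**Working it through.** The plan gives no figure of its own on this point. Its one design figure, N = 70 (section 5.1), cannot be reproduced because power and test are not stated; nothing below tests it. The documents also give no reliability *r*, baseline-to-follow-up correlation *ρ* or practice gain *d*. All three are assumptions, shown as ranges.

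**1. Precision of the arm contrast.** Assume equal variance σ² at baseline and follow-up.

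- Change score, variance per patient: 2σ²(1−ρ)
- ANCOVA, residual variance per patient: σ²(1−ρ²)
- Ratio ANCOVA/change: (1+ρ)/2
- Extra patients needed by the change score for equal precision: 2/(1+ρ) − 1

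| ρ | Change, σ² | ANCOVA, σ² | Variance saved | Extra patients | Power, change | Power, ANCOVA |
|---|---|---|---|---|---|---|
| .5 | 1.00 | 0.75 | 25% | 33% | .400 | .505 |
| .7 | 0.60 | 0.51 | 15% | 18% | .597 | .667 |
| .8 | 0.40 | 0.36 | 10% | 11% | .770 | .812 |
| .9 | 0.20 | 0.19 | 5% | 5% | .968 | .975 |

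Power is for an assumed 0.5 SD difference between two arms, 70/3 = 23.3 per arm, two-sided 5%, without Bonferroni adjustment. This treats all 70 as Parkinson's patients; if the 70 include healthy controls, the arms are smaller.

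**2. Chance baseline imbalance.** The SD of the baseline difference between two arms is √(2/23.3) = 0.29 SD. An imbalance of that size shifts a change-score contrast by (1−ρ) × 0.29: 0.15 SD at ρ = .5, 0.09 at .7, 0.06 at .8 and 0.03 at .9. ANCOVA removes this shift.

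**3. RC against an SD-unit z-score.** RC = change / (SD × √(2(1−r))) and z = change / SD, so RC/z = 1/√(2(1−r)).

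| r | √(2(1−r)) | RC/z | RC of 1.96, in SD |
|---|---|---|---|
| .5 | 1.000 | 1.00 | 1.96 |
| .7 | 0.775 | 1.29 | 1.52 |
| .8 | 0.632 | 1.58 | 1.24 |
| .9 | 0.447 | 2.24 | 0.88 |

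The two agree only at r = .5.

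**4. Practice and individual calls.** Assume a cut-off of 1.96 (the plan states none), no true change and a practice gain of *d* SD. Then P(flagged improved) = 1 − Φ(1.96 − d/√(2(1−r))). With d = 0 this is 2.5%. With d = 0.3:

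- r = .7: 1 − Φ(1.96 − 0.387) = 5.8%
- r = .8: 1 − Φ(1.96 − 0.474) = 6.9%
- r = .9: 1 − Φ(1.96 − 0.671) = 9.9%

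**5. Practice and the arm contrast.** A shift common to all arms cancels from the difference in means. A simulation of three arms of 22 with r = .8 and 5,000 runs gave type I error of .046, .048 and .055 for shifts of 0, 0.3 and 0.5 SD, all near the nominal 5%.

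**The case against.** The strongest reply is that nothing here makes the arm comparison invalid. That is correct. Change scores are unbiased under randomization, and at ρ of .8 or .9 the variance saving is only 10% or 5%. The point is one of efficiency. What remains is that the saving costs no patients and becomes material at lower ρ.

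A reader might also draw three stronger conclusions, which the documents do not support.

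- **Patients were misclassified because change was divided by the raw SD.** The sentence before the inaccurate one ties RC to reliability, and a raw-SD score would not use reliability at all. The likeliest reading is a loose gloss on the SD of the difference. Had the raw SD been used with a 1.96 cut-off, the two-sided false-flag rate would have been 1.1% (r = .7) or 0.2% (r = .8), which is too strict; but the plan states neither.
- **The sign rule fails on timed tests, where a higher value is worse.** The plan gives no subtraction formula. It defines orientation by outcome: "Positive scores indicate an improvement in performance, and negative scores indicate a worsening of performance". There is no contradiction.
- **Practice biases the therapy comparison.** The randomized arms share one test schedule, so a common gain cancels. One limit applies: section 6 lets patients change group after a completed course. If second-course data were used, which the plan does not say, prior test exposure could differ between arms.

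The no-therapy arm is also an imperfect practice reference. In a progressive disease its 6-month change mixes practice with decline.

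**Conclusion.** The point holds as a loss of precision, a wrong description and an incomplete specification. It does not show bias or error in the classification of patients.

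Comparing randomized arms on RC scores by ANOVA gives up 5% to 25% of the contrast variance for ρ from .9 to .5, and leaves in the effect of chance baseline imbalance. This assumes equal variances, one scaling per test, and that the ANOVA named for group differences is also the test applied to the RC scores.

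The sentence equating RC with an SD-unit z-score is inaccurate for any reliability other than .5. Uncorrected practice affects only individual calls of improvement: 2.5% becomes 5.8–9.9% under an assumed 0.3 SD gain and r from .7 to .9.

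**What to change.** - Compare the three randomized arms by ANCOVA of the follow-up score on therapy and baseline score, or by a mixed model over 4 weeks and 6 months with baseline as covariate. Label it post hoc: the last patient left on 29.06.2018, and the plan, last updated 09.10.2019, describes its analyses as done. Report it beside the RC-based result.
- Keep RC for describing individuals. Replace the z-score sentence with the formula, RC = change / (SD × √(2(1−r))), and state for each test the SD used, the reliability and its source, and the cut-off.
- For individual calls, subtract the mean change in the no-therapy arm, or show the calls with and without that correction. Say that at 6 months this mean also contains disease progression. The subtraction leaves the arm contrast unchanged.

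The cost is a re-analysis and a few sentences. The baseline scores are already collected, the covariate uses one degree of freedom, and no patients are needed. The real price is that the adjusted comparison can no longer be presented as prespecified.

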Clinical Study Protocol

Title:

Effectiveness of specific and intensive speech-language therapy on verbal fluency decline and verbal apraxia symptoms in patients with Parkinson's disease with and without Deep Brain Stimulation (DBS) – a randomized single-blind controlled trial.

Acronym: EILT (Evaluation of Intensive Language Therapy)

EKNZ Nr: 2016-01 428

Clinicaltrial.gov. NR: NCT 029 358 42

Document Created: 30.11.2015

Ethical Approval Obtained: 13.09.2016

Study Start/ First Patient IN: 19.09.2016
Last Patient OUT: 29.06.2018

Study End: 22.10.2018

Final Document update: 09.10.2019

Study Synopsis

1. Background and Rationale:	
In the course of Parkinson's disease (PD) speech and language (SL) deficits may often emerge. In addition, severe verbal fluency (VF) decline has been repeatedly observed in the context of deep brain stimulation (DBS) in PD. While PD non-DBS patients have deficits with respect to loudness and intelligibility of their voice, PD patients who have undergone DBS (PD-DBS) tend rather to suffer from difficulties in semantic and phonemic word retrieval, and from speech apraxia symptoms. However, to-date and to the best of our knowledge, therapeutic approaches focusing specifically on SL deficits observed in PD-DBS patients are yet to be developed and evaluated regarding their effectiveness.

2. Objective(s):	
To evaluate the effectiveness of a high frequency and specific SL therapy compared to an unspecific, non-verbal sham intervention (rhythmic balance-mobility-training (rBMT)), as well as to a 'no therapy'-condition.
 
In more detail:
 
 (1) To compare rhythmic speech and gait of PD-DBS and PD non-DBS patients after different intensive rhythmic intervention programs (rSLT, rBMT and no therapy), as well as against healthy controls (HC) directly after the intervention and again in 6 months (short and long-term effects). 
Secondary objectives:
 
 (1) To examine how speech and language abilities alter due to Parkinson Disease's (PD) by comparing PD-DBS, PD non-DBS and HC (all groups are age-, gender and education-matched). (2) To examine the effect of rhythmic interventions on cognitive abilities. (3) To evaluate measures derived from functional Near Infrared Spectroscopy (fNIRS) as a prognostic marker for verbal and cognitive outcome in PD patients with and without DBS over a period of time.

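### Section 7 provides for group ANOVAs with no stated score or visit, then for group comparisons on RC scores, each at .05, and does not say which decides the therapy question; if both use follow-up data, the false-positive chance per endpoint and visit is about 9% to 10%.

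*Combined protocol and SAP*

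**What the plan says.** The section headed 7. Statistical Analysis has two layers of group comparison.

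- The first: "To calculate group differences (i.e. rSLT, rBMT, NT, HC) several univariate ANOVA with post-hoc Bonferroni corrections were performed". No score (raw, follow-up or change) and no visit is given. Bonferroni is attached only to the post-hoc comparisons.
- The threshold: "The level of statistical significance was set at $p < .05".
- The second begins with "Changes in performance were analyzed with the reliable change score (RC" and explains that "scores are compared on a participant-individual level (e.g. BL with 4 weeks FU, and BL with 6 months FU". RC is put on a standardised scale: "the reliable change score is equivalent to computing a z-score based on standard deviation units". The section then states "Further group comparisons are based on the RC scores", without naming the test, any correction or the role of these comparisons.

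Two other places bear on how the first layer should be read. Objective (1) in the synopsis compares the intervention groups with each other, "as well as against healthy controls (HC) directly after the intervention and again in 6 months (short and long-term effects". Section 6 (Randomization) says of the controls: "Group 4 were healthy elderly, who did not receive any therapy and participated once".

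**The concern.** Objective (1) asks for group comparisons at the two follow-up times. The ANOVAs in section 7 name the three therapy conditions and are not limited to baseline. The RC comparisons are introduced as further ones. On that reading, each endpoint at each follow-up visit has two between-group tests: one on the follow-up score and one on the change from baseline. Each is at the full .05, and either could be reported as the therapy effect.

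The post-hoc Bonferroni correction deals with pairs of groups. It does not deal with a choice between two outcome scales. At stake are the error rate behind a claim of benefit and, when the two tests differ, which of them answers the primary objective.

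**Working it through.** **What there is to reproduce.** The documents give no joint error rate for the two analyses, only .05 per test. N = 70 in section 5.1 does not bear on this point except to suggest arm sizes.

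**Inputs from the documents.** Alpha .05 per test (section 7); three arms randomised 1:1:1 (section 6); total N = 70 with about 5 drop-outs expected (section 5.1).

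**Assumptions.**
- Arm size is not stated. If the 70 are all patients, (70 − 5)/3 = 21.7, so 22 per arm. If the 70 include healthy controls in four equal groups, 70/4 = 17.5, so 17 per arm.
- The baseline to follow-up correlation ρ is not stated. The range used is .3 to .9.
- Data are normal with equal variances, and each patient counts once. Section 6 lets patients swap groups after a completed tranche; that is a separate matter and is not modelled.
- RC is change divided by one constant per measure. Its F-test is then identical to the F-test on raw change.

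**Step 1: how related the two tests are.** With baseline Y0 and follow-up Y1 of unit variance, Cov(Y1, Y1 − Y0) = 1 − ρ and Var(Y1 − Y0) = 2(1 − ρ). So

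corr(Y1, Y1 − Y0) = (1 − ρ)/√[2(1 − ρ)] = √[(1 − ρ)/2].

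This is .59 at ρ = .3, .50 at .5, .39 at .7, .32 at .8 and .22 at .9. The tests overlap only partly, and less as ρ rises.

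**Step 2: ceiling.** Two independent tests at .05 give 1 − .95² = .0975.

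**Step 3: simulation.** Three arms, 100,000 trials per setting, one-way F-tests on follow-up and on change, each at .05. The first two result columns have no therapy effect; the last two have one arm 0.8 SD higher at follow-up.

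| ρ | At least one false positive, 17 per arm | Same, 22 per arm | Verdicts differ, 17 per arm | Same, 22 per arm |
|---|---|---|---|---|
| .3 | 9.0% | 9.0% | 32.8% | 29.5% |
| .5 | 9.2% | 9.2% | 32.3% | 25.7% |
| .7 | 9.4% | 9.5% | 33.4% | 23.1% |
| .8 | 9.5% | 9.4% | 35.0% | 23.3% |
| .9 | 9.7% | 9.7% | 35.8% | 23.1% |

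Each test alone rejects in about 5% of null trials. Arm size hardly affects the null columns. With one arm 1.0 SD higher, the verdicts differ in 16% to 25% of trials (17 per arm) or 7% to 18% (22 per arm).

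**Step 4: the other readings of the ANOVAs.**
- Baseline scores only: the ANOVA does not address therapy, so the therapy error per endpoint and visit stays at 5%.
- Change scores: the ANOVA and the RC comparison are the same F-test, so the error again stays at 5%.

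**Step 5: healthy controls in the ANOVA.** They took part once, so they have no RC score, and the two layers cannot cover the same four groups. With 17 per group and no therapy effect, a four-group ANOVA that sets patients' follow-up scores beside the single control measurement rejects in 27%, 63% or 84% of trials if controls differ from patients by 0.5, 0.8 or 1.0 SD. Its overall F is not a clean test of therapy.

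**Step 6: one deciding test.** An ANCOVA of follow-up on arm and baseline rejects in about 5% of null trials. At 17 per arm, ρ = .5 and one arm 0.8 SD higher, its power is 76% to 77% across simulation runs, against 64% for the follow-up test or the change test alone. At ρ = .9 it matches the change test. As an alternative, running both tests at .025 gives a joint error of .047 (ρ = .5) or .049 (ρ = .8).

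**The case against.** A reader might infer that the plan tests the same therapy question twice and so nearly doubles its error rate. The documents do not establish that. Section 7 states no score or visit for the ANOVAs, and it assigns change in performance to RC. Healthy controls, listed in the ANOVAs, took part once. Secondary objective (1) compares PD-DBS, PD non-DBS and healthy controls and needs no follow-up data. A natural reading is therefore that ANOVA describes group differences, controls included, and RC carries the therapy effect. The word introducing the RC comparisons may mean no more than subsequent.

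This stands as far as it goes: the inflation is conditional, and the supportable range is 5% to about 9.75%. It does not remove the point. Objective (1) does ask for group comparisons after the intervention and at 6 months, so the follow-up reading is open too, and the text does not settle which was meant.

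The statement that the two tests often disagree also needs a limit. It is fair for moderate effects and weaker at 1.0 SD.

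Finally, the study has ended. Naming a deciding test now cannot by itself restore error control for results already seen, and an ANCOVA appears nowhere in the documents, so it would be a new analysis and more than a change of wording.

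**Conclusion.** The concern holds in conditional form. Section 7 describes two sets of group comparisons at .05, leaves the score and visit of the first unstated, and names neither as deciding the therapy question.

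If both are run on follow-up data from the randomised arms, the false-positive chance is about 9% to 10% per endpoint and visit, roughly 1.8 to 1.9 times the stated level. In that case a 0.8 SD benefit in one arm gives conflicting verdicts in about 23% to 36% of trials, depending on arm size and correlation. If the ANOVAs were for baseline only, or used change scores, there is no inflation. The sizes rest on the assumed correlation, arm sizes and normal data; the gap in the text does not. They apply to one endpoint at one visit and do not cover the further multiplicity across endpoints and visits.

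**What to change.** 1. For each endpoint and follow-up visit, let one between-arm analysis decide: an ANCOVA of the follow-up score on arm with the baseline score as covariate, in the three randomised arms only. Keep healthy controls in the baseline comparison.
2. Report any follow-up-score ANOVA and the RC group comparisons as supportive, with no separate significance claim.
3. State which scores and visits the ANOVAs that were run used. Only those who ran them can supply this, and it should not be presumed.
4. Because the study end (22.10.2018) and the final document update (09.10.2019) have passed, record the ANCOVA as a dated change, and label it post hoc if it was chosen after the data were seen.

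The cost is one additional analysis on data already collected, plus the text changes. The downside is that RC comparisons can no longer carry a claim alone.
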